7.3.2 Qualitative Measure

Qualitative research methods consistent with those outlined in the FDA draft guidance "Patient-Focused Drug Development: Methods to Identify What is Important to Patients" will be employed in conducting and analysing participant interview data. Semi-structured interviews with some open-ended questions will be conducted in a subset of those participants who present with Long COVID syndrome. Narrative responses will be coded by identifying and classifying distinct concepts and proceeding with interviews until concept saturation is achieved. This effort is designed to assure that the above questionnaires have adequately captured Long COVID syndrome, and if not, to inform enhancements to these questionnaires for subsequent trials.

8 STUDY SCHEDULE OF ASSESSMENTS

The Schedule of Assessments is provided in [Table 3](#).

[illegible]

Abbreviations: AE = Adverse Event, ECG = electrocardiogram, MRI = magnetic resonance imaging.

1. Can be same as Day 1.
2. Every attempt should be made to conduct the Day 28 Visit (+3d) and the Day 40 Visit (± 2 d) on site to ensure collection of all study safety assessments. Remote conduct of the Day 28 and Day 40 Visits (i.e. via Telehealth) will be considered by the sponsor on a case by case basis.
3. The vital signs should be taken at approximately the same time each day, preferably between 12pm-5pm.
4. Data for all routine 12-lead ECGs performed while the participant is an inpatient will be captured on the CRF. Additionally, the Day 28 and Day 40 12-lead ECG can be omitted if this visit is conducted remotely.
5. Testing for COVID-19 needs to have been performed and a positive result obtained within 28 days of Screening.

6. If laboratory evaluations are performed more than once a day as part of the routine management of hospitalized COVID-19 patients, the results from the first set of daily labs collected will be reviewed for this study and entered in the CRF. Safety clinical laboratory samples will be analysed by the investigational site's local pathology laboratory.
7. Pregnancy test (urine or serum) will be performed for women of childbearing potential at screening.
8. Blood sample to check TNF levels will be collected prior to dosing with study drug on Day 1. This lab will be analysed at the investigational site's local pathology laboratory.
9. Blood sample to perform anti-drug antibody (ADA) test will be collected prior to dosing with study drug on Day 1. ADA samples will also be collected at Day 28 and Day 40. This lab will be collected at the site and shipped to the central laboratory for analysis.
10. The second dose of study drug will be administered on Day 8, if participant is still in hospital.
11. The Screening WHO Ordinal Scale will be completed any time after informed consent and up to 1-hour post-randomization on Day 1. The scale will then be completed daily during the afternoon hospital rounds until participants are discharged from hospital. The scale will also be collected on Day 28 and Day 40.
12. Participants will be assessed for development of disease progression from randomization to Study Day 40.
13. Concomitant medications and AEs will be recorded for all participants who are randomized until Study Day 70.
14. Participants may complete Long COVID questionnaires via ePRO (participants) or paper pencil (informants) between Study Day 40-50.

9 STATISTICAL METHODS

9.1 Determination of Sample Size

A total sample size of 366 participants randomized 1:1 to treatment with either INB03 + SOC or Placebo + SOC (N=183 in each arm) will provide adequate power to compare the proportion of participants with disease progression in each group by Day 28. It is assumed that 21% of enrolled participants randomized to Placebo + SOC will progress whereas the expected disease progression rate will be reduced by two-thirds to 7% in participants randomized to INB03 + SOC. To observe the expected treatment effect, N=346 (N=173 per arm) are required.

Additionally, an interim analysis for futility will be performed when approximately 20% of participants required to observe the expected treatment effect complete the Study Day 28 visit (N~70). Participants evaluated in the interim analysis include those who are randomized and receive study drug and have the Day 28 assessment or who had an intercurrent event prior to Day 28. Imputation of missing data will be performed as described in [Section 9.5.1](#). A custom Z-statistic boundary will be used to assess futility.

The proposed study with the above assumptions will have at least 90% power assuming a one-sided Z-Test with $\alpha=0.005$.

9.2 Statistical and Analytical Plans

Details of statistical parameters and methods to be used will be described in a Statistical Analysis Plan (SAP). The SAP will be developed and finalized prior to database lock and unblinding. The SAP will describe details regarding the statistical methodology to assess differences between treatment groups, all data handling procedures and definitions, including further details on the methods used for managing missing data.

9.3 Analysis Populations

The analysis populations are as follows:

9.3.1 Intent-to-treat (ITT)

All participants who have signed informed consent, meet inclusion/exclusion criteria, are enrolled in the study and who are randomized to a treatment arm will be included in the ITT population. The ITT will be the analysis population for disposition and demographic reporting purposes. Analyses will be based on the randomized treatment.

9.3.2 Modified Intent-to-treat (mITT)

The modified ITT population is a subset of the ITT population and includes participants who have received any amount of INB03 or Placebo. The mITT will be the primary analysis population for all efficacy reporting purposes. Analyses will be based on the randomized treatment.

9.3.3 Per-Protocol Set (PPS)

All participants included in the ITT population with no major protocol deviation will comprise the PPS. The PPS will be a secondary analysis population for select efficacy endpoints. Analyses will be based on treatment received.

9.3.4 Safety Set (SS)

All participants who have received any amount of INB03 or Placebo are included in the safety set. The SS will be the analysis set for safety reporting and will be based on treatment received (INB03 or Placebo).

9.4 Statistical Methods

Statistical analyses will be performed using SAS 9.4 or higher. In general, continuous variables will be summarized using number of participants (n), mean, standard deviation (SD), median, minimum, and maximum. Categorical variables will be tabulated with frequency counts and percentages. All summary tables will be presented by treatment arm. Where appropriate, 95% confidence intervals (CIs) will be provided. All data will be listed.

Hypothesis testing of the primary efficacy endpoint will be performed based on a one-sided test with $\alpha=0.005$

Any changes in the protocol planned analyses will be described and documented in the SAP and/or clinical study report.

9.5 Efficacy Endpoints

Statistical analysis for the primary efficacy endpoint will be performed with a one-sided $\alpha=0.005$ level of significance. Secondary endpoints will also be analyzed, however no adjustment for multiplicity is planned for the secondary endpoints. Therefore, nominal p-values will be provided for the secondary efficacy endpoints. Analyses and summary statistics will be based on the mITT population. Sensitivity and other supplemental analyses may be repeated in other analysis populations.

9.5.1 Primary Endpoint

The primary estimand will be estimated based on the mITT population and includes randomized participants who have been diagnosed with COVID-19, have at least one co-morbidity, are admitted to the hospital and have pulmonary complications due to COVID-19 who receive any amount of study drug. To estimate this estimand, all post-randomization data up until Day 28 of the study will be used in the evaluation of treatment difference regarding disease progression. The estimator is the proportion of participants with disease progression up until Day 28 post-randomization where disease progression defined as is administration of mechanical ventilation or death.

As specific intercurrent events may occur that could lead to missing or spurious data, the following strategies will be used.

- Participant withdraws consent and has missing disease progression data: The “Treatment Policy” strategy for this event will be employed. The last available post-randomization record of the WHO Ordinal Scale for Clinical Improvement will be used to identify disease progression. If mechanical ventilation or death data are missing from the database, and if the last available post-randomization score is 7 or greater, the participant will be considered to have disease progression for the primary analysis of the primary endpoint.
- Participant is lost to follow-up and have no hospital discharge date and data regarding disease progression is missing: The “Composite” strategy for this event will be used. Participants with this intercurrent event are considered to have disease progression. This strategy assumes participants who remain in the hospital but are lost to follow-up for any reason are assumed to have disease progression. Similarly, participants who are discharged from the hospital and do not have information collected up to Day 28 are assumed to have disease progression.
- Participant is lost to follow-up and has a hospital discharge date and data regarding disease progression is missing: The “Treatment Policy” strategy for this event will be employed. The last available post-randomization record of the WHO Ordinal Scale for Clinical Improvement will be used to identify disease progression. If mechanical ventilation or death data are missing from the database, and if the last available post-randomization score is 7 or greater, the participant will be considered to have disease progression for the primary analysis of the primary endpoint.
- In the rare circumstance where a participant who is not lost to follow-up and did not withdraw consent and whose data regarding disease progression is missing: The “Treatment Policy” strategy for this event will be employed. As disease progression is also collected through the WHO Ordinal Scale for Clinical Improvement, if mechanical ventilation or death data are missing from the database, the last post-randomization record of WHO Ordinal Scale for Clinical Improvement will be used to support the disease progression endpoint. If a score of 7 or higher is recorded, the participant will be considered to have disease progression for the primary analysis of the primary endpoint.

All participants will have a binary value of 0 or 1, where:

- 0=No disease progression
- 1=Disease progression

Descriptive statistics will be presented for the number and percent of participants with disease progression by Day 28.

The analysis method used to compare treatment groups INB03 + SOC and Placebo + SOC will be a stratified Cochran-Mantel-Haenszel (CMH) test. Stratification factors of Age (≤ 50 , >50 to 65 , >65) and number of co-morbidities (1, 2, 3+) will be included to compare the response rate of INB03 + SOC to Placebo + SOC. Treatment differences will be compared using $\alpha=0.005$ one-

sided significance level and odds ratios (ratio of odds in INB03 + SOC arm to the odds in Placebo + SOC only arm) and the 95% confidence interval will be provided. If expected, cells counts are not sufficient for each strata, strata levels may be combined for the analysis.

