3 OBJECTIVES AND PURPOSE

3.1 Primary Objective

The primary objective of the study is to:

- Evaluate if INB03 given as a SC injection can decrease disease progression defined as death or requirement for mechanical ventilation in participants with pulmonary complications from COVID-19 infection.

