4.2 Study Endpoints

4.2.1 Primary Endpoint

The primary endpoint of the study is:

- Proportion of participants with disease progression from randomization to 28 days post-randomization, where disease progression is defined by the development of need for mechanical ventilation or death. Mechanical ventilation includes CPAP, BIPAP or mechanical ventilation requiring intubation.

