7.2.1 Disease Progression

Participants will be assessed from randomization to 40 days post-randomization for development of disease progression defined as:

- **Need for mechanical respirator support:** If a participant has progressed from passive oxygen support (nasal canula, face mask, etc) to needing something that is attached to an active device/machine (eg: CPAP), this is considered as needing mechanical respirator support.
- **Death:** Time, date and cause of death should be recorded.

Additionally, participants will be assessed for the following non-respiratory complications of COVID-19 from randomization to Day 40:

- **Transfer to ICU level care:** In the midst of a surge, the definition of an ICU may be stretched to include cardiac care unit (CCU), step-down unit or any place that has been set up to receive patients that may need mechanical ventilation. ICU level care is defined as a hospital setting where patient to nurse ratio is ≤ 4 .
- **New onset myocardial infarction (MI) or congestive heart failure (CHF):** the development of CHF or MI once enrolled in the study is made by standard clinical/laboratory/imaging modalities based on the best judgement of the clinical team. The development of congestive heart failure or new myocardial infarction will often initiate some sort of medical intervention.

- **Requirement for renal replacement therapy:** The decision to initiate renal replacement therapy is made by the clinical team. Renal replacement therapy means any form of dialysis including intermittent or continuous peritoneal or hemodialysis.
- **New onset neurologic symptoms:** Any neuropsychiatric symptom that requires medical intervention qualifies. This can be, but is not limited to, stroke, encephalopathy, seizures, hallucination and coma. Neuropsychiatric symptoms caused by hypoxia or hypotension are not considered a COVID-19 related neurologic symptom.
- **New onset thrombotic or embolic event:** The development of venous or arterial thrombosis or embolus that requires medical intervention that occurs after enrollment is new onset. Thrombosis of peripheral or central venous access, arterial lines or dialysis catheters is not considered a thromboembolic event endpoint.

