6.2.1 Primary Efficacy Endpoint and Analyses

The primary objective of the study is to evaluate the effect INB03 + SofC has on disease progression compared with placebo + SofC. Disease progression is defined as death or requirement for mechanical ventilation in participants with pulmonary complications from COVID-19 infection. The primary endpoint to assess the objective is to compare the proportion of patients who reach disease progression in both treatment arms. Disease progression will be assessed up to Day 28. Patients will be identified as follows:

1 = Disease progression – defined as developing the need for mechanical ventilation or death by Day 28. Mechanical ventilation includes CPAP, BIPAP, or mechanical ventilation requiring intubation.

0 = No disease progression – defined as not developing the need for mechanical ventilation or death by Day 28

The null hypothesis is that there is no difference in the proportion of patients who have disease progression between treatment groups and the alternative is that the proportion of INB03 treated patients with disease progression is less than the proportion of placebo patients with disease progression.

$$H_0: P_{INB03} = P_{Placebo} \text{ vs } H_1: P_{INB03} < P_{Placebo}$$

Statistical analysis of the primary endpoint will be performed with a one-sided level of significance and final alpha of $\alpha=0.005$.

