6.2.1.1 Primary Estimand

Treatment Arms	INB03 (1mg/kg) + SofC and Placebo + SofC, given via subcutaneous injection.
Target Population	Randomized participants who have been diagnosed with COVID-19, have at least one co-morbidity, are admitted to the hospital and have pulmonary complications due to COVID-19 who receive any amount of study drug.
Endpoint	Proportion of participants with disease progression from randomization to 28 days post-randomization. Disease progression is defined by the development of need for mechanical ventilation or death. Mechanical ventilation includes CPAP, BIPAP or mechanical ventilation requiring intubation.

Population Summary	Difference between treatment arms in proportion of disease progression by day 28	
Analysis Method	Stratified Cochran-Mantel-Haenszel	
Intercurrent events	Event	Strategy
	Withdraw consent prior to Day 28	While on treatment – data prior to event is of interest
	Lost to Follow-up prior to Day 28 with no hospital discharge date	Composite variable – event is considered informative about patient's outcome
	Lost to Follow-up prior to Day 28 with a hospital discharge date	Treatment policy – data is used as if event never occurred
	Did not receive Dose 2 on Day 8	Treatment policy – data is used as if event never occurred
	Discontinued from study for reasons other than Withdrawal of consent or Lost to Follow-up prior to Day 28	Treatment policy – data is used as if event never occurred
	Receipt of prohibited medication prior to Day 28	Treatment policy – data is used as if event never occurred
	Did not receive mechanical ventilation due to unavailability	Hypothetical – data is used assuming event did not occur

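### The primary event is ventilation given in Protocol 9.5.1 but ventilation needed in the objective, endpoint section and SAP, and the SAP's unavailability rule behaves as if receipt counts

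*Protocol*

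**What the plan says.** Most of the plan defines the ventilation component by clinical need:

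- Protocol 3.1 (objective): "disease progression defined as death or requirement for mechanical ventilation".
- Protocol 4.2.1 (endpoint): "where disease progression is defined by the development of need for mechanical ventilation or death".
- Protocol 7.2.1 (what sites assess): progression from passive oxygen to "needing something that is attached to an active device/machine".
- SAP 6.2.1 (the value coded 1): "defined as developing the need for mechanical ventilation or death by Day 28".
- SAP 6.2.1.1 (estimand endpoint): "Disease progression is defined by the development of need for mechanical ventilation or death".

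Protocol 9.5.1, which sets out the primary estimand and its estimator, departs from this: "disease progression defined as is administration of mechanical ventilation or death".

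The SAP has one rule for ventilation that was not received. SAP 6.2.1.1 lists the intercurrent event "Did not receive mechanical ventilation due to unavailability" with a hypothetical strategy. SAP 6.2.1.3 handles it as missing data, using the last WHO ordinal score before the event. SAP 6.1.2 also names non-receipt because no machine was available as a major deviation. Neither document has a rule for a participant who needed ventilation but did not receive it for another reason, such as declining it or having a treatment limit.

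**The concern.** Needing ventilation and being given it are different facts, and the sponsor anticipated that they could diverge, since it wrote a row for one way in which they do. Where they diverge in a participant who survives to Day 28, the primary outcome is 1 under one section and 0 under another. The trial is small and the primary outcome is binary, so a few such classifications could matter. If the choice of definition is still open when unblinded results reach the data monitoring committee and selected sponsor staff, it could be made, or appear to be made, with knowledge of the result.

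**Working it through.** **Step 1. Who changes status.** Take a participant judged to need CPAP, BIPAP or intubation by Day 28.

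- Received it: event under both wordings.
- Did not receive it and died by Day 28: event under both, through the death component.
- Did not receive it and was alive at Day 28: event under need (Protocol 4.2.1, SAP 6.2.1), non-event under administration (Protocol 9.5.1).

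Only the third group is affected.

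**Step 2. Does the SAP settle it?** Follow a participant in the third group whose ventilator was unavailable.

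- By the coding rule in SAP 6.2.1 the need has developed, so the value is already 1 and nothing is missing.
- SAP 6.2.1.3 nevertheless lists non-receipt as a possible source of missing outcome data and turns to the last WHO score before the event.
- The SAP gives no cut-off for that score. Protocol 9.5.1 uses 7 or more in its own WHO-score rules. In the protocol appendix, scores 7 to 9 describe ventilation in use and 10 is death. A participant not yet ventilated would normally score 6 or lower and be coded 0.
- The hypothetical label points the other way. Had a ventilator been available, this participant would presumably have been ventilated and counted.

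So the SAP's wording, its data rule and its strategy label do not agree for the one non-receipt case it covers.

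**Step 3. The plan's own figures.** Protocol 9.1 assumes 21% on placebo and 7% on INB03, with 173 per arm, one-sided alpha 0.005 and 90% power. The unpooled normal formula gives

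(2.576 + 1.282)² × (0.21 × 0.79 + 0.07 × 0.93) / 0.14² = 175.4, or 176 per arm,

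close to 173. Exact binomial power at 173 per arm is 0.902. The sample size is not in question, and these rates are used below only as planning assumptions.

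**Step 4. Size in the trial as it stopped.** SAP 6.2.4 reports 79 randomized and 77 dosed. Assume an even split (38.5 per arm) and the planning rates.

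- Placebo: 38.5 × 0.21 = 8.1 events.
- INB03: 38.5 × 0.07 = 2.7 events.
- Total: 77 × 0.14 = 10.8 events.
- One participant reclassified: 1 / 10.8 = 9% of all expected events. By arm, that is 1 / 8.1 = 12% of the placebo events or 1 / 2.7 = 37% of the INB03 events.

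The rates in the interim section (20% and 12.5%) give 77 × 0.1625 = 12.5 events, and one participant is then 8%.

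The size of the third group is not given. If, purely as an assumption, it made up 0%, 10% or 20% of events, it would contain 0, about 1 (10.8 × 0.10) or about 2 (10.8 × 0.20) participants.

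**The case against.** The best answer is that the SAP governs the analysis and says need. Protocol 9.2 hands data handling and definitions to the SAP, and the SAP's objectives table, coding rule and estimand are consistent with the protocol's endpoint and assessment sections. The single word *administration* sits in an ungrammatical sentence and may be a slip. Under the SAP's wording, a participant who needs ventilation and declines it has already met the endpoint, so no intercurrent-event rule is required to count that person.

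Much of this stands. It confines the literal contradiction to one protocol section and makes need the likely intention. It does not close the point. Protocol 9.4 asks for changes to the planned analyses to be documented in the SAP or study report, and SAP 1.1 lists its changes without this one. The unavailability row also remains: it is an SAP rule, not a protocol slip, and it would normally code as 0 a participant whom the SAP's own definition codes as 1.

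Three stronger readings are tempting and are not supported:

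- *That power falls from 90% to about 83%.* A reader could obtain such figures by assuming that the administration wording misses up to one event in seven. The documents give no such rate, part of any needed-but-not-given group dies and counts anyway, and the calculation describes 346 treated participants when enrolment closed with 77 dosed.
- *That the 21% and 7% rates cannot fit both definitions.* They can if the affected group is empty or very small. The sample-size text in the synopsis speaks of respiratory failure or death and does not say which definition produced the rates.
- *That participants ventilated only for a procedure would be miscounted.* Nothing in the documents suggests this occurs, and Protocol 7.2.1 frames the event as progression from passive oxygen.

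**Conclusion.** The inconsistency is real and concerns the definition of the primary event. It affects only participants who needed ventilation, did not receive it and were alive at Day 28. Their number is unknown and may be zero, so neither a loss of power nor a direction of bias can be stated. What can be said is how much each one weighs: about 9% of the roughly 11 events expected among the 77 dosed. That rests on the 21% and 7% planning rates and an even split between arms; observed rates would change it. The documents reviewed do not show whether the case report form records need separately from receipt. If it does not, the definitions could also differ in what the database can support. The point should be fixed because it touches the primary outcome and costs little, but it does not by itself put the trial's conclusion in doubt.

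**What to change.** Settle the following before any unblinding, including the preliminary analysis planned ahead of final database lock:

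1. In Protocol 9.5.1, replace *administration* with the development-of-need wording already used in Protocol 4.2.1 and SAP 6.2.1 and 6.2.1.1. If the protocol will not be amended again, record in SAP 1.1 that the need definition applies.
2. Change the unavailability row in SAP 6.2.1.1 and 6.2.1.3 so that a participant recorded as needing ventilation but not receiving it, for any reason, is coded as progression. Drop the fallback to the earlier WHO score for these participants.
3. Add one sensitivity analysis that counts only delivered ventilation or death, and report how many participants differ between the two definitions, by arm.

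The cost is minor wording changes and one extra analysis. This concerns how outcomes are classified and changes nothing in patient care.
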